4.3.1. Study discontinuation (if applicable) N/A

4.3.2. Concomitant medication (if applicable) N/A

4.4. Risks and Benefits

There should be minimal side effects or discomfort associated with participating in this research study. One potential risk of participation for participants is loss of confidentiality

and privacy. However, when we collect identifying data, unique code numbers will always replace patient names in the research database. Locked file cabinets will be used to store materials with identifying information. Participants may refuse any part of study participation.

Cognizant of the potential risks to privacy in social media research, we will follow methodological and ethical considerations for recruitment and intervention delivery published by thought leaders including [name].⁵⁵ The present trial will follow the formal safety and monitoring guidelines for researchers using social media outlined by Russomanno and colleagues (2019)⁴⁸ through protocols defining FB page administration, notification settings and monitoring, recruitment cycle duration, inclusion and exclusion terms, and public page settings and moderation.⁴⁸ These guidelines are described below:

Defining Facebook Page Administration. The FBTA will be posted through publicly accessible Facebook pages associated with the study PI's research lab. To ensure adequate monitoring of the FBTA, at least 2 research team members ([name], PI and [name], Research Project Associate) will be assigned as administrators of the page and advertisement settings.

Notifications. To assure continuous monitoring, all page and advertisement administrators will have the Facebook app downloaded to their mobile phones prior to beginning study recruitment and ensure that all notifications and interactions with the recruitment advertisement are being monitored.

Recruitment Cycle Duration. Advertisements should be posted for, at maximum, 7 days per cycle to minimize burnout to research study staff during recruitment.

Inclusion and Exclusion Terms. To target the Facebook advertisements to the study population of interest, researchers should use inclusion and exclusion terms based on study criteria.

Public Page Settings and Moderation. Researchers may restrict who can post directly to the public Facebook page by turning off the Visitor Posts feature in order to ensure only page administrators can post directly to the public site.

An additional side effect considered to be minimal and far outweighed by the potential benefits of participating in this study is participants may find it stressful to answer questions regarding their smoking history and behaviors especially in the context of lung cancer screening. If an individual reports significant distress, an appropriate referral will be made.

We do not expect any adverse events because of this intervention.

5 – Methods

5.3. Study intervention (including schedule of events and study visits)

Participants randomized to *LungTalk* or non-tailored video will watch the web-based online videos and then complete study assessments as per the schedule of assessments in Section 5.5. Please see below for a full description of the study intervention.

LungTalk (<https://www.lungtalkhmh.org/>) is a 10-15 minute long computer-tailored health communication and decision-making tool that is theoretically grounded in the Conceptual Model on Lung Cancer Screening Participation.⁴¹ This model links the Health Belief Model to the Precaution Adoption Process Model and includes key psychological variables (e.g., stigma, mistrust, fatalism, fear and worry) as factors that may influence an individuals' decision to screen, or not, for lung cancer.⁴¹ The tool as a whole serves as a cue to action for a screening-eligible individual to engage in a discussion with their primary care clinician about the option to screen, or not, for lung cancer. *LungTalk* is an interactive computer program that includes audio, video, and animation segments with tailoring algorithms for scripts presented from a master content library.¹⁰ *LungTalk* tailors initially on smoking status. Our prior research revealed individuals who used to smoke feel further stigmatized when messaging is crafted as if they still smoke. Early in the program, the user is asked to indicate if they currently smoke or if they quit smoking and the content has been adjusted to respect an individuals' current smoking status. In addition, during the study start-up phase (prior to participants being enrolled), *LungTalk*'s master content library will be enhanced to tailor content based upon personal barriers to lung screening. The top 5 barriers (*cost, worry, lack of symptoms, time, stigma*) have been identified in our recently completed study testing the Conceptual Model on Lung Cancer Screening from the perspective of the individual (R15 CA208543). Using a similar process as performed in prior studies of which [name] was Co-I (R01CA196243; MPIs: Paskett/Champion; PCORI IHS-1507-31333; PI: [name]), Drs. [name], [name], and [name] will create brief video clip testimonials with dedicated in-house resources using MSK Information Technology who manage and maintain *LungTalk* programming and servers to address each barrier. These short (~2-3 min) video clips will be embedded into the master content library and tailoring algorithms added to the master programming of *LungTalk*. After the lung scan video, a brief modified version of the Perceived Barriers to Lung Cancer Screening Scale will be administered on screen. Based upon the users' identification of personal barriers (i.e., cost, worry about finding something, lack of symptoms or current lung issues, lack of knowledge about the screening process, stigma), *LungTalk* will tailor to those specific barriers with the brief video clip testimonials from the master content library. Following this component, *LungTalk* concludes by offering the option of saving or printing a tailored print-out at the end for individuals to use as a discussion prompt with their primary care clinician.¹⁰ This print-out highlights key points related to lung health and screening tailored by smoking status, offers question prompts the user can use to initiate a discussion with their primary care clinician, and tailors based upon questions that remain important to the user that they wish to discuss further with their primary care clinician.¹⁰ Messaging in *LungTalk* is presented at an 8th grade level, and in

consideration of different ways people like to learn, the content is presented via narration as well as key text on screen.¹⁰

GO² Foundation for Lung Cancer Lung Screening Informational Video (ADD LINK) is a non-tailored educational brochure and link to the video, *Screening Saves Lives! Learn More About Low Dose CT Lung Cancer Screening* produced by the GO² Foundation for Lung Cancer that will be delivered via emailed or texted link to the participant.

5.4. Assignment / randomization (if applicable)

After eligibility is confirmed in REDCap, participants will be registered in the CTMS system. Upon completion of baseline assessment, participants will be randomized using the REDCap randomization module to one of the two arms (i.e., LungTalk or non-tailored GO² video) using a stratified block design stratifying by smoking status (current vs former). Stratified random assignment will ensure the two groups are comparable in distribution on smoking status, a salient variable for lung screening behavior noted in our prior work.^{9,17,41} Consolidated Reporting of Randomized Clinical Trials (CONSORT) guidelines for RCTs will be followed.

5.5. Section of instruments (to include for all studies with a social behavioral intervention)

Table 1. Measures and Timepoints of Assessment

Constructs	Assessment or Measure	# of Items	Time to Complete (min)	Validated?	Baseline (T1)	1 Wk Follow-Up (T2)
Eligibility	Screening Survey	3	1	N		
Demographics	Demographic and Health Status Characteristics	20	5	N	X	
Knowledge	Knowledge: Lung Cancer Screening	9	5	N	X	X
Perceived Risk	Perceived Risk of Lung Cancer Scale ¹⁶	3	1	Y	X	X
Perceived Benefits	Perceived Benefits of Lung Cancer Screening Scale ¹⁶	6	3	Y	X	X
Perceived Barriers	Perceived Barriers to Lung Cancer Screening Scale ¹⁶	17	10	Y	X	X
Self-Efficacy	Self-Efficacy for Lung Cancer Screening Scale ¹⁶	9	5	Y	X	X
Occurrence of a Patient-Clinician Discussion	Self-report of Occurrence of a Patient-Clinician Discussion about Lung Cancer Screening	1	1	N	X	X
Screening Uptake	Self-report via the stages of adoption algorithm for screening with verification process	1	1	N	X	X
Upcoming PCP Visit	Self-report of upcoming visit with	1	1	N	X	X

	primary care provider scheduled				
1. Screening Survey	TOTAL TIME		32 minutes	27 minutes	

will be used to determine eligibility. See Section 4.3.b above for details.

2. **Demographic and Health Status Characteristics** will be assessed using items we have used in prior studies. These include age, gender, race/ethnicity, education level, income level, perceived financial status, insurance status, marital status, employment status, smoking status (if former, how long since quit in months), and family history of lung cancer.
3. **Total Knowledge of Lung Cancer Screening** will be assessed with a 9-item multi-dimensional scale used in our preliminary study adapted from literature specific to lung cancer.¹⁶ Several aspects will be assessed, including knowledge of lung cancer, risk, and screening. The range of scores is 0 to 9.
4. **Lung Cancer Screening Health Belief Scales** described in the preliminary studies section will be used to measure perceived risk, perceived benefits, perceived barriers, and self-efficacy. Content and construct validity have been established. Internal consistency reliability was established by our team with a sample of 497 screening-eligible long-term smokers:
 - i. *Perceived Risk of Lung Cancer* is a 3-item scale with Likert-type responses. The range of scores is 3 to 12 (higher perceived risk of lung cancer). Cronbach's α was 0.88 in our preliminary study.¹⁶
 - ii. *Perceived Benefits of Lung Cancer Screening* is a 6-item scale with responses ranging from 1=strongly disagree to 4=strongly agree. The range of scores is 6 to 24 (higher perceived benefits) with a Cronbach's α of 0.76 in our preliminary study.¹⁶
 - iii. *Perceived Barriers to Lung Cancer Screening*. This scale has 17 items with four-point Likert responses where 1=strongly disagree and 4=strongly agree. The range of scores is 17 to 68 (higher perceived barriers) with a Cronbach's α of 0.87 in our preliminary psychometric study.¹⁶
 - iv. *Self-Efficacy for Lung Cancer Screening*. This scale has 9 items with a four-point Likert response option to assess individual beliefs about ability to arrange and complete an LDCT to screen for lung cancer. The range of scores is 9 to 36 (higher levels of self-efficacy) with a Cronbach's α of 0.92 in our preliminary psychometric study.¹⁶
5. **Occurrence of a Patient-Clinician Discussion about Lung Cancer Screening** will be assessed with a single item requiring dichotomous (Y/N) response: Have you had a discussion with your primary care clinician about lung cancer screening?
6. **Lung Cancer Screening Uptake** is the primary outcome and will be assessed via self-report via the stages of adoption algorithm for lung screening. The algorithm for collecting this item presents additional questions conditional on responses (see Appendix D). There are seven stages (*unaware, aware but unengaged, undecided, decided not to act, decided to act, action, and maintenance*). This will help to understand screening behavior more robustly by understanding the stages of decision-making and adoption (i.e., uptake) of the behavior. Please note that screening uptake is considered stages 6 and 7 (action and maintenance).

The description of lung cancer screening with LDCT of the chest developed in our preliminary studies includes a picture and a written description of an LDCT. This description is embedded in the follow up surveys (Appendix C) prior to the self-reported question to ensure participants understand the question. Using the same successful procedure as in our prior pilot RCT for LungTalk,⁴⁵ we will verify screening for individuals who self-report completing an LDCT of the chest to screen for lung cancer by mailing an authorization form to be signed and mailed back to the research office. Trained research staff will verify the screening LDCT scan using the information and signed authorization form by contacting the facility directly to request confirmation.

7. **Upcoming Primary Care Provider Visit** will be measured with one item: Do you have an appointment already scheduled to follow-up with your primary care provider? If yes, when?

In order to generate a robust semi-structured interview guide about the sustainability of a social media-based approach to increasing lung screening awareness and uptake, key stakeholder participants representing administrators (healthcare system and screening centers), key screening center personnel, advocacy organizations (i.e., LUNGevity, Dusty Joy Foundation), and national organizations (American Cancer Society, American Lung Association, GO₂ Foundation for Lung Cancer) will be conducted. We will begin the Key Stakeholder participant recruitment no earlier than Year 3 of the study. These stakeholder participants will complete one semi-structured interview that will take 45-60 minutes to complete. We will amend the protocol to include the semi-structured interview guide that will be informed and created from the quantitative data collected from the participants.

FB Analytics. Using the FB analytics component⁴⁶ of our FBTA, our assessment plan will measure the total reach of the FBTA to increase awareness of the option to screen for lung cancer among screening-eligible individuals.⁴⁷ Quantitative data collected from FB analytics during the recruitment campaign will assess reach by detailing: 1) reach; 2) link clicks; and 3) impressions.⁴⁶ Reach in FB analytics is defined as the number of people who saw the FBTA at least once.⁴⁶ This can be further analyzed by hour, day, specific number of days, week, and campaign length. In addition, reach can be further stratified by specific location (i.e., state, city, town, county, zip code).⁴⁶ Table 1 defines key Facebook analytics for this study. In addition, Facebook will provide the number of people who meet the target profile, within each location.

Table 1. Key Facebook Analytics to Assess Reach	
Facebook Analytic	Definition
Reach ⁴⁶	Total # of people who saw the FBTA at least once.
Link Clicks ⁴⁶	Total # of clicks on the link within the FBTA that led to the REDCap survey platform of the study.
Impressions ⁴⁶	Total # of times the FBTA was on screen (may include multiple views of the ad by the same person/people).

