While lung screening is recommended by the U.S. Preventive Services Task Force (USPSTF),^{1,2} has the potential to detect lung cancer at earlier, more treatable stages, has a 20% lung cancer-related mortality reduction in long-term smokers^{3,4} and is covered by Medicare and other health insurers,⁵ population uptake has been abysmal. It has been 9 years since the USPSTF released its recommendation, yet less than 5% of screening-eligible Americans have been screened.⁶ Screening-eligible individuals are generally unaware of early detection of lung cancer.⁷⁻⁹ Given that high-risk individuals are not aware that lung screening exists, it is essential to employ novel community-focused strategies to increase awareness about lung screening so as to reach high-risk, screening-eligible individuals. Social media offers untapped opportunities to address the lack of awareness and knowledge that stymie lung screening uptake. Because Facebook (FB) has the ability to target advertisements to individual users by key demographic and interest areas within their profile, Facebook-targeted advertisement (FBTA) offers an ideal platform to target and deliver a public-facing, tailored health communication and decision support intervention to increase awareness of, and knowledge about, lung screening among those most at risk. To facilitate both awareness of the option to screen and meaningful patient-clinician discussions about screening, effective communication strategies are needed to prepare patients to initiate (“Ask your doctor”) and to have these important discussions with their primary care clinician. To foster both, our team has developed LungTalk,¹⁰ a novel computer-tailored health communication and decision support tool to (1) increase awareness and knowledge about lung screening; (2) decrease perceived barriers to screening based upon misinformation; and (3) increase screening rates among individuals whose decision after a shared decision-making discussion with their primary care clinician is to screen. LungTalk currently tailors on smoking status because our prior research revealed individuals who used to smoke feel further stigmatized when messaging is crafted as if they still smoke. The current version of LungTalk has been pilot tested and indicated that tailored information for lung screening more than doubled total knowledge scores regarding lung cancer risk and screening compared to a non-tailored lung screening information sheet. In addition, our prior work also revealed the top barriers screening-eligible individuals face when considering lung screening. Therefore, during the first 9 months of the study (prior to any participants being enrolled), refinements to the master content library of LungTalk will be undertaken with our internal IT team at MSK to insert video testimonials for perceived barriers to lung screening and algorithms for the perceived barriers

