5.7. Follow-up and end-of study (if applicable) n/a

5.8. Statistical Method

This behavioral intervention study will randomize 500 screening-eligible individuals in a 1:1 ratio into the *LungTalk* intervention or the non-tailored video intervention condition. We will use descriptive statistics such as means, standard deviations, and frequency distributions/distributional assumptions to examine data quality, identify patterns of missing and out-of-range values, and evaluate parametric assumptions. Remediation of normal distribution assumption violations will be accomplished using the Box-Cox procedure for transformations. We will apply the intention-to-treat (ITT) principle in handling missing data on screening uptake; a study participant will be coded as 'no screening uptake' unless otherwise verified by our participation sites. We will examine violations of the missing-at-random assumption for secondary outcomes. If missingness is associated with any

observed characteristics, then covariates associated with missingness will be incorporated into a sensitivity analysis to minimize bias.

Aim 1. Examine the use of a social media platform (i.e., Facebook) to reach high-risk individuals eligible for lung screening. We will describe and compare the following measures and metrics using a mixture of data from FB analytics and study data from REDCap.

Goal	Analytic Plan
Estimate the number and percentage of individuals aged 50 and older who currently or formerly smoke in the population that the advertisement is marketed.	Numerator = # of Facebook members age 50+ who currently or formerly smoke in target markets Denominator = total # of Facebook members in target markets Both numerator and denominator provided by FB Analytics.
Estimate the approximate percent of this population to which this advertisement is marketed are eligible for lung screening according to the USPSTF guidelines.	Numerator = # of eligible participants, among those screened. Denominator = total number screened. Data from screening survey.
Record the percent of eligible participants who agree to participate in the study.	Numerator = total number consented Denominator = # of eligible participants
Compare differences between those participating and those not participating on smoking status (i.e., current vs. former), age, gender, geography, and other key variables collected on the screening survey.	Descriptive tables along with a series of independent samples t-tests and Chi-square tests.

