Record reasons that participants refuse to participate in the study.	Descriptive analysis from screening survey data.
Estimate attrition at 1 week and 6-month follow-up time periods.	Numerator = # of baseline participants - # of participants who complete the follow-up assessment (either 1 week or 6 month) Denominator = # of baseline participants Completion at follow-up defined as completing, at the least, the screening/stage of adoption item.
Compare differences between those completing and those not completing the study on sociodemographic and health status variables, geography, baseline scores on knowledge, lung cancer screening health beliefs, and stage of adoption for lung cancer screening.	Descriptive tables along with a series of independent samples t-tests and Chi-square tests. Completion of the study is defined as completing the screening uptake item for the 6-month assessment.

Aim 2. Compare the effectiveness of a computer-tailored health communication and decision support tool (LungTalk) to a non-tailored Lung Screening Informational Video on lung screening: 1)

knowledge; 2) health beliefs (perceived risk, perceived benefits, perceived barriers, self-efficacy); 3) occurrence of a patient-clinician discussion about lung screening; and 4) uptake and completion (primary outcome). Total knowledge scale scores and Lung Cancer Screening Health Beliefs (total scale scores for perceived risk, perceived benefits, perceived barriers, self-efficacy) are continuous variables. Occurrence of patient-clinician discussion and screening uptake are dichotomous variables. Prior to group comparisons, measures will be described by timepoint, both overall and by group. Within-group changes will be assessed using standardized effect sizes. The primary outcome is screening uptake at 6-month follow-up. For between-group comparisons, generalized linear models will be used with adjustment for smoking status; appropriate link functions for each outcome will be determined based on distributions (e.g., for dichotomous outcome variables we will use a logit link). In the case of differential attrition, as noted above, a sensitivity analysis will be conducted such that regression models will also include baseline covariates that differ significantly between participants who do and do not complete follow-up assessments.

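### Secondary outcome, low-cost improvement: unless the follow-up survey adds a time window, the discussion item compares 'ever discussed', and the planned model leaves the baseline answer unused

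*Combined protocol and SAP*

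**What the plan says.** Section 5.5, item 5 gives the whole measure: "Have you had a discussion with your primary care clinician about lung cancer screening", answered yes or no, with no recall period or anchor date. The baseline table in section 4.3.c and Table 1 in section 5.5 both list "Self-report of Occurrence of a Patient-Clinician Discussion about Lung Cancer Screening" at baseline; Table 1 lists it again at 1 week. The baseline answer precedes assignment (section 5.4): "Upon completion of baseline assessment, participants will be randomized using the REDCap randomization module".

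The exclusion criteria in section 4.2.2 remove people with a previous screening LDCT, a followed nodule, lung cancer or impaired decision-making. They do not remove people who have already discussed screening.

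Under Aim 2 in section 5.8 the outcome is dichotomous, and for the comparison of arms "generalized linear models will be used with adjustment for smoking status". Baseline answers are used in three other ways. First, "measures will be described by timepoint, both overall and by group". Second, within-group change is expressed as standardised effect sizes. Third, if missingness depends on observed characteristics, "covariates associated with missingness will be incorporated into a sensitivity analysis to minimize bias"; the Aim 2 text has a similar provision for differential attrition.

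**The concern.** Section 5.3 says that LungTalk "serves as a cue to action for a screening-eligible individual to engage in a discussion with their primary care clinician". The effect of interest is therefore a discussion that happens after the tool is used. A person who talked with a clinician before joining can truthfully answer yes at follow-up whichever arm they are in. Such answers add the same expected number of events to both arms and carry no information about the intervention. They pull the two proportions together and move the odds ratio towards 1.

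Uptake is largely protected from this because prior LDCT is an exclusion. The discussion outcome has no such protection. At stake are the size and meaning of a secondary effect estimate and some of its power, when the answer that would separate earlier discussions is already collected before randomisation.

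**Working it through.** **1. The plan's own figure.** Section 5.8.2 states 80% power for 25% vs 15% uptake with 250 per arm, two-sided 5%. The two-proportion formula with pooled variance under the null gives 80.0%, so the same formula is used below. The plan gives no rate, effect or power for the discussion item.

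**2. Inputs.**
- n = 200 per arm: the allowance for 20% missing data in section 5.8.1, stated there for knowledge and perceived risk and borrowed here.
- b, the share answering yes at baseline: not in the documents; assumed 2% to 20%.
- p1 and p2, the rates of a first discussion among baseline-no participants: not in the documents. Three assumed pairs are used: 40% vs 25%; 25% vs 15% (borrowed from the uptake assumption); 10% vs 5% (possible if the item is analysed at 1 week).

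**3. Dilution.** If every baseline yes is repeated, the observed rate in an arm is b + (1-b)p, so the observed difference is (1-b)(p1-p2). For 40% vs 25% and b = 10%:
- LungTalk: 0.10 + 0.90 × 0.40 = 46.0%
- Video: 0.10 + 0.90 × 0.25 = 32.5%
- Difference: 13.5 points instead of 15
- Odds ratio: (0.46/0.54) / (0.325/0.675) = 1.77 instead of 2.00

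**4. Power.** Power = Φ{[p1-p2 - 1.96·√(2p̄(1-p̄)/n)] / √([p1(1-p1)+p2(1-p2)]/n)}, where p̄ is the mean of the two rates. Continuing the example:
- As planned (n = 200; 46.0% vs 32.5%; p̄ = 0.3925): (0.135 - 1.96 × 0.04883)/0.04836 = 0.81, so power is 79%.
- Baseline-no only (n = 180; 40% vs 25%; p̄ = 0.325): (0.15 - 1.96 × 0.04937)/0.04873 = 1.09, so power is 86%.

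| First-discussion rates | b | 'Ever' rates | OR, 'ever' (first) | Power as planned | Power, baseline-no |
|---|---|---|---|---|---|
| 40% vs 25% | 2% | 41.2% vs 26.5% | 1.94 (2.00) | 88% | 89% |
| 40% vs 25% | 5% | 43.0% vs 28.8% | 1.87 (2.00) | 85% | 88% |
| 40% vs 25% | 10% | 46.0% vs 32.5% | 1.77 (2.00) | 79% | 86% |
| 40% vs 25% | 20% | 52.0% vs 40.0% | 1.63 (2.00) | 67% | 82% |
| 25% vs 15% | 2% | 26.5% vs 16.7% | 1.80 (1.89) | 66% | 70% |
| 25% vs 15% | 5% | 28.8% vs 19.3% | 1.69 (1.89) | 60% | 68% |
| 25% vs 15% | 10% | 32.5% vs 23.5% | 1.57 (1.89) | 52% | 66% |
| 10% vs 5% | 2% | 11.8% vs 6.9% | 1.80 (2.11) | 39% | 47% |
| 10% vs 5% | 5% | 14.5% vs 9.8% | 1.57 (2.11) | 31% | 46% |

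**5. Imperfect repetition.** If only 90% of baseline yes answers are repeated, b is replaced by 0.9b in the dilution formula. For 40% vs 25%, power as planned becomes 85%, 80% and 70% at b = 5%, 10% and 20%, close to the table.

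**6. Check with the planned model.** Logistic regression on arm and smoking status was simulated (3,000 runs, 200 per arm, 40% vs 25%, b = 20%). With full repetition, power was 67.4% as planned, 81.9% among baseline-no participants and 81.9% with everyone plus the baseline answer as a covariate. With 90% repetition it was 68.7%, 80.9% and 80.7%. With equal 25% rates in both arms, all three analyses rejected in 4.2% to 5.4% of runs (b from 5% to 20%, 80% to 100% repetition).

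**The case against.** The strongest reply is that the fielded question cannot be seen. Section 5.5, item 6 places the follow-up surveys in Appendix C, which is not among the pages available, and item 5 gives one wording for a question asked more than once. A window at follow-up would remove the 'ever discussed' problem and leave only a preference for baseline adjustment. This stands, and the point is conditional on it.

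The baseline share may also be small. Section 1 says "Screening-eligible individuals are generally unaware of early detection of lung cancer", and prior LDCT is excluded. This stands in part. At 40% vs 25% and b = 2% the loss is about one point. At lower discussion rates a small b costs more: eight points at 10% vs 5% with b = 2%. The borrowed 25% vs 15% is an uptake assumption and sets no lower limit for discussions, particularly within one week.

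A reader might infer that the baseline answer isolates all new discussions. It does not: it isolates first discussions among people who had none. Someone who talked earlier but was never screened is still a proper target of the tool, and their repeat discussion is captured only by a time window.

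A reader might also infer that the existing baseline uses already solve the problem. Description by timepoint would reveal b, and within-group effect sizes would show change, but neither alters the between-arm test. The missing-data provisions could bring the item into a model, but only as a sensitivity analysis triggered by missingness or attrition.

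**Conclusion.** The point holds as a modest improvement to a secondary outcome, on the condition that the follow-up item has no time window. The risk difference for first discussions is then multiplied by about (1-b). Across the assumed scenarios the loss of power runs from about 1 point (40% vs 25%, b = 2%) to about 15 points (40% vs 25% with b = 20%, or 10% vs 5% with b = 5%). All the rates, b and the use of 200 per arm are assumptions, so these figures illustrate the mechanism and do not predict the trial's loss.

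It would be tempting to call the planned comparison biased or invalid. The documents do not support that. Randomisation follows the baseline assessment, so earlier discussions are balanced in expectation; the simulated type I error is close to 5%; and 'ever discussed' by arm is a valid though diluted contrast. The primary outcome, uptake, is unaffected, and no stated power figure is wrong.

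The timepoint also needs stating. The visible Table 1 shows this item at baseline and 1 week only, whereas section 4.1.1 and the Aim 1 and Aim 2 text in section 5.8 also describe a 6-month follow-up. A column may have been lost when the text was extracted, so this calls for clarification and is not by itself an error in the plan.

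**What to change.** In section 5.8, Aim 2, name the timepoint at which discussion is analysed. Then take the route that matches the fielded question.

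- **No window at follow-up.** Add: *Occurrence of a first patient-clinician discussion will be compared between arms among participants who answered no to this item at the pre-randomisation baseline, using the logistic model adjusted for smoking status. The all-participant comparison of ever having had a discussion will be reported beside it.*
- **A window exists, or can be added before follow-up begins** (for example, since completing the study program). Print it in section 5.5, analyse all participants and add the baseline answer as a covariate. This also captures repeat discussions. Rewording after follow-up has started would mix two versions of the item.

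Without a window, keeping everyone and adding the baseline answer as a covariate gives nearly the same arm estimate. If every baseline yes is repeated, however, that covariate's own coefficient cannot be estimated, so the restricted analysis is cleaner.

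The cost is two or three sentences in the plan and, optionally, one changed REDCap item. No extra data, visits or participants are needed. The downside is that the restricted result applies only to people without an earlier discussion and does not count repeat discussions, which is why the all-participant result should stay beside it. The choice should be fixed before outcome data by arm are seen.
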